procedures based on external tattoos and room lasers. A free- breathing trace of the Calypso transponders will be obtained to allow the patient to settle on the treatment table and to study real-time respiratory traces. The patient will then be asked to perform a therapist-coached modified slow vital capacity maneuver and DIBH maneuver [1] and hold their breath. Patients will have the ability to perform this maneuver with or without biofeedback from digital goggles that are placed over the patient's eyes and display the breathing trace of the Calypso transponders. The use of the digital goggles will be determined by patient preference or at the discretion of the treatment team. This will allow us to investigate whether real-time biofeedback adds to the reproducibility of patients holding their breath. A DIBH cone-beam CT will be acquired in approximately three breath-holds, once a week for standard fractionated RT patients or with each fraction for SBRT patients. After review and approval of the images, the patient will be treated while holding their breath using the DIBH maneuver. In standard fractionated RT patients the radiation treatment will be guided by the external tattoos and daily 2D kV imaging. The Calypso transponder signal will be used to monitor the level of the breath-hold during treatment. The breath-hold level based on the Calypso transponder signal will be verified daily by the 2D imaging and once a week in 3D by the DIBH cone-beam CT. In SBRT patients, the radiation treatment will be guided by the external tattoos and daily DIBH cone-beam CT. The Calypso transponder signal will be used to monitor the level of the breath-hold during treatment. The therapists will monitor the respiratory trace signal from the Calypso transponders throughout the treatment and will initiate the radiation treatment delivery when the patient holds his/her breath within the tolerance level the patient has been assigned to. This will be continued up until the initially planned 30 patients are accrued.. Should the transponder signal indicate that the target has moved outside of the preset tolerance, the therapists will hold further radiation treatment delivery until the patient's breathhold has returned to the desired target range or until the patient's setup has been corrected. In the additional 25 patients planned, the margins will be reduced in a step-wise fashion. The gate will be decreased 1mm per each set of 5 patients until the duty cycle (beam-on time) and number of DIBH attempts are doubled. The gate at which this occurs will be considered the minimum clinically feasible gate

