4.0 OVERVIEW OF STUDY DESIGN/INTERVENTION

4.1 Design

The primary objective of this study is to evaluate the feasibility of Calypso transponders as an internal tumor surrogate to guide DIBH radiation treatments in real time.

The use of Calypso transponders has the potential to result in improved reproducibility of tumor positioning during DIBH treatments. We therefore plan to analyze the obtained respiratory traces from the Calypso signal as well as the imaging data from CBCTs and radiographs to explore a set of secondary objectives. These include a comparison of the reproducibility of DIBH tumor position with visual versus without visual biofeedback (for patients who agree to use the digital goggles), measurement of any residual intrafraction tumor motion, improvement in normal tissue dosimetry during DIBH based on the Calypso lung transponder signal as a surrogate, and determination of any increase in dose escalation and the potential for decreasing margins made possible by Calypso-guided DIBH. Given the successful radiation localization in the first 25 patients, we will also aim to determine the minimum clinically feasible gate margin for radiation. We will reduce the gate from +/-5mm by 1mm for every 5 patients treated. Once the minimum gate is determined, the remaining patients will be treated at +1mm from this value. We will also plan to enroll at least 10 additional conventionally fractionated patients to assess the impact of tumor shrinkage on beacon position and centroid changes. Finally, lung volume preservation will be assessed on wide field of view cone-beam CTs and compared intra- and interfraction within each patient to check for reproducibility or variability of lung volumes across multiple DIBH maneuvers.

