5. The patient will be remotely asked to repeat the DIBH maneuver and a CBCT will be obtained over several breathholds (exact number depending on the patient's ability to hold their breath) using partial arcs and the assigned breath hold tolerance window.
6. The CBCT images will be evaluated and the patient will be repositioned for a soft tissue match as needed. The soft tissue match will then be evaluated and approved by the treating physician as is our normal clinical process. The isocenter coordinates in Calypso will be changed based on the patient's repositioning shift dictated by the CBCT soft tissue match. No more than 2 CBCTs per treatment will be done for protocol purposes.

The patient will then be remotely asked to reproduce the DIBH maneuver with the tolerance window to which they have been assigned and be treated in DIBH. Number of beam holds, treatment interruptions and total treatment time from first beam-on time to the last beam-off time will be recorded by the therapists. Beacon position during DIBH will be monitored by the therapist to assure that the patient maintains the DIBH position throughout the treatment delivery. If the Calypso beacon signal indicates that the tumor has moved outside of the tolerance window, the radiation beam will be automatically held by the system and resumed when the target is within range.

9.2 For patients undergoing standard fractionated RT the following procedures will be performed:

1. Standard setup procedures based on external tattoos will be performed.
2. The Calypso antenna will be deployed and positioned over the patient's chest. Tracking of the Calypso transponder signal will commence.

Optional: In patients where the Calypso antenna external markers detected by an in-house infrared tracking system can be arranged in such a way that both signals can be obtained

simultaneously (depending on body habitus), a free-breathing trace of the Calypso transponders over 2 minutes in combination with the external marker signal will be obtained . These will be used for future analysis and building of an external/internal respiration model.

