To determine the minimum clinically feasible gate margins we will decrease the gate in a step-wise progression as far as a minimum of 2 mm. The gate will be reduced from +/- 5mm by 1mm for every 5 patients treated. Halving of the duty cycle will be considered the minimum gate that is clinically feasible. Once the minimum gate is determined, the remaining patients will be treated at +1mm from this value.

In the additional 10 conventionally fractionated patients, tumor shrinkage will be summarized as relative shrinkage in a percentage. Beacon position and centroid are 3D coordinates that will be determined as a distance from a landmark such as a bone or the carina.

Lung volume preservation will be assessed on wide field of view cone-beam CTs and compared intra- and interfraction within each patient to check for reproducibility or variability of lung volumes across multiple DIBH maneuvers.

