For the 1st secondary objective, we will compare the visual vs no visual biofeedback treatments (for patients who agree to use the digital goggles) by the number of treatment interruptions. We expect that there will be fewer treatment interruptions when using biofeedback. To this end Wilcoxon signed-rank tests will be conducted based on the patients who can successfully be treated.

For the 2nd secondary objective, we will assess differences in the ability of maintaining the DIBH maneuver within the fate with and without visual biofeedback. Such differences will be measured as duty cycle, and will be compared using Wilcoxon signed-rank tests based on the patients who can successfully be treated.

For the 3rd secondary objective, the residual intrafraction tumor motion (surrogated by Calypso) will be measured in all 3 dimensions and the euclidean distance will be calculated, which will then be correlated with the normal tissue dosimetry (see end of Section 12.0). Patients will receive multiple fractions and thus multiple measurements of such distance will be obtained from the same patients.

These repeated measures will be averaged for each patient and the correlation will be examined by simple linear regression. If such continuous data are skewed, we may either use an appropriate monotone transformation, or examine the nonparametric correlation coefficient (such as Spearman rank correlation coefficient) between the tumor motion and the normal tissue dosimetry instead.

For the 4th secondary objective, the potential increase in dose escalation and decrease in margins made possible by Calypso- guided DIBH, as contrasted to those obtained from the 40 CT scan, will be formulated as pair data from each patient and tested by using Wilcoxon signed-rank tests. Dosimetric parameters listed at the end of Section 12.0 will be used again for such analysis.

The 5th secondary objective does not require statistical analysis. See Section 12.0 for details.

For the 6th secondary objective, tumor shrinkage, beacon position and centroid changes in conventionally fractionated patients (totally 10), all measured as continuous variables, will be summarized descriptively.

For the 7th secondary objective, intra- and inter-fraction variation in lung volume preservation of multiple DIBH maneuvers will be recorded within each patient and summarized descriptively.

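### Sections 1 and 12 give different stopping rules for narrowing the gate, and no section says what follows if the rule is not met at 2 mm

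*Combined protocol and SAP*

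**What the plan says.** The extension of 25 patients is meant to find the smallest workable gate. Section 4.1 gives the start and the step: "We will reduce the gate from +/-5mm by 1mm for every 5 patients treated". Two sections then say when to stop.

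- **Section 1 (Protocol Summary):** the gate comes down "until the duty cycle (beam-on time) and number of DIBH attempts are doubled", and "The gate at which this occurs will be considered the minimum clinically feasible gate". Section 1 gives neither a floor nor a rule for later patients.
- **Section 12:** "we will decrease the gate in a step-wise progression as far as a minimum of 2 mm"; the trigger is "Halving of the duty cycle will be considered the minimum gate that is clinically feasible"; then "Once the minimum gate is determined, the remaining patients will be treated at +1mm from this value". It sets no condition on the number of attempts.

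Section 14 adds no method: "The 5th secondary objective does not require statistical analysis. See Section 12.0 for details". Sections 4.1 and 9.0 repeat the stepwise reduction without a trigger. All of this is current text.

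**The concern.** The trigger is the whole method for the 5th secondary objective. It fixes the minimum gate that will be reported and, through the +1 mm rule, the gate at which later extension patients are treated. With two triggers in force, the same data could give two answers. They differ in the stated direction of change in duty cycle (doubled or halved) and in whether breath-hold attempts must also double.

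There is a second, independent gap. The +1 mm rule depends on a minimum having been determined. If patients cope well at every step and the trigger has not fired at 2 mm, the text states neither the minimum gate nor the gate for the patients still to be treated.

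**Working it through.** The plan gives no numerical target for this objective, so there is no figure to reproduce. The check has three parts.

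**1. Can the two triggers mean the same thing?** Three readings of the Section 1 wording:

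- *Usual definition (beam-on time divided by elapsed delivery time).* With beam-on time fixed, halving duty cycle doubles elapsed time. Taking 0.30 as an assumed starting value, halving gives 0.15, while doubling gives 0.60, which is more efficient delivery. From an assumed 0.60, doubling gives 1.20, which is impossible. A narrower gate would not be expected to double duty cycle, so the Section 1 rule would not fire.
- *Beam-on time, as Section 1 glosses it.* Section 4.1 leaves the dose prescription unchanged. At a fixed dose rate (assumption), beam-on time would not double either.
- *Delivery time.* Section 12 loosely describes duty cycle as quantifying the time delivery takes. On this reading, doubled time is the same event as halved duty cycle. Section 1 still requires attempts to double as well, so it can stop only at the same gate as Section 12 or a narrower one.

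**2. When do the rules diverge on the delivery-time reading?** Let a be the ratio of attempts to their value at ±5 mm, and c the ratio of breath-hold cycle time (hold plus rest). With beam-on time fixed and elapsed time equal to attempts × cycle time:

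duty-cycle ratio = 1 / (a × c), so duty cycle halves when a × c = 2, that is c = 2/a.

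| Attempts ratio a when duty cycle halves | Cycle-time ratio c needed |
|---|---|
| 2.0 | 1.00 |
| 1.9 | 1.05 |
| 1.8 | 1.11 |
| 1.5 | 1.33 |

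If cycle time is unchanged, the two rules fire together. Illustration with assumed values (120 s of beam, 20 s holds, 30 s rest, so a 50 s cycle):

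- 15 s usable per hold: 8 attempts, 400 s, duty cycle 30%.
- 7.5 s usable per hold: 16 attempts, 800 s, duty cycle 15%. Both criteria are met at once.

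Section 12 stops first only if cycles lengthen as the gate narrows.

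**3. How many patients would be affected?** Inputs: five sets of 5, 1 mm steps, remaining patients at the stopping gate + 1 mm. I apply the 2 mm floor to both rules and take ±5 mm as the reference, so no stop occurs at 5 mm. The text does not settle whether the first set is treated at 4 or 5 mm, so both are shown.

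| Stop at | Gates by set, first set at 4 mm | Gates by set, first set at 5 mm |
|---|---|---|
| 4 mm | 4, 5, 5, 5, 5 | 5, 4, 5, 5, 5 |
| 3 mm | 4, 3, 4, 4, 4 | 5, 4, 3, 4, 4 |
| 2 mm | 4, 3, 2, 3, 3 | 5, 4, 3, 2, 3 |
| none | 4, 3, 2, ?, ? | 5, 4, 3, 2, ? |

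Comparing rows, with Section 12 stopping first and Section 1 later but by 2 mm:

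| Section 12 / Section 1 stop | Patients with a different gate, 4 mm start | 5 mm start |
|---|---|---|
| 4 / 3 mm | 20 | 15 |
| 4 / 2 mm | 20 | 15 |
| 3 / 2 mm | 15 | 10 |

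The differences are 1 to 3 mm per patient and 1 to 2 mm in the reported minimum.

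If Section 12 stops and Section 1 never does, as its literal wording implies, the comparison is with the last row of the gate table. For a Section 12 stop at 4, 3 or 2 mm, 10, 5 or 0 patients have a different stated gate under either start. In addition, the last 25 − 15 = 10 patients (4 mm start) or 25 − 20 = 5 (5 mm start) have no gate under Section 1.

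The no-stop gap in Section 12 itself involves the same 10 or 5 patients.

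**The case against.** The strongest reply is that this is loose wording in a summary. Section 1 glosses duty cycle as beam-on time and Section 12 treats it as a measure of delivery time, so both probably mean that treatment takes twice as long. Section 14 already sends the reader to Section 12, the only section that gives trigger, floor and +1 mm rule together. This largely stands: Section 12 is the likely intended rule. It does not remove the attempts condition, which appears only in Section 1, or the lack of a usable definition of duty cycle.

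Divergence is also unproven. It needs longer breath-hold cycles, on which the documents give no data. The opposite is plausible too: if a tighter gate produces more aborted, shorter attempts, attempts double before duty cycle halves and both rules stop together. This stands, and it makes the patient counts conditional maxima.

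On the no-stop gap, the 2 mm floor could be read as the default minimum, which with the +1 mm rule puts the remaining patients at 3 mm. That is a reasonable inference, but it is not written down.

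Finally, a reader might infer from Section 9.0, where beam holds, "treatment interruptions and total treatment time from first beam-on time to the last beam-off time will be recorded by the therapists", that duty cycle cannot be computed because beam-on time is not listed. The documents do not support that. Calypso signals are recorded at treatment, traces are analysed afterwards, and the beam is held automatically outside the window, so time in gate may be derivable.

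**Conclusion.** The inconsistency is real and should be corrected before the extension is analysed. Section 1 and Section 12 do not state the same stopping rule under any of the three readings, and the rule sets both a reported result and later patients' gates. The affected number ranges from none (delivery-time reading, unchanged cycle length) to 20 of 25 with a first set at 4 mm, or 15 of 25 with a first set at 5 mm. These counts assume sets of 5, the 2 mm floor and stops by 2 mm under both rules. The missing outcome at 2 mm holds whichever way duty cycle is read.

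Two stronger conclusions are tempting. One is that the protocol deliberately sets opposite criteria; its own descriptions of duty cycle make careless wording more likely. The other is that most extension patients will be treated at a wrong gate, or that the trial's main conclusion is at risk. The documents give no likelihood for divergence, every gate at issue lies between 2 and 5 mm, and the primary feasibility test does not use the gate rule.

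**What to change.** - **Section 1:** replace the trigger with the Section 12 rule and drop attempts as a stopping condition.
- **Section 12:** define duty cycle as beam-on time divided by elapsed delivery time, and replace the loose description there. Stop when a set's duty cycle is at or below half its ±5 mm value. Say which patients supply that value, how it is summarised over a set of 5, and whether the first set is treated at 4 or 5 mm.
- **No stop at 2 mm:** add one sentence saying that the minimum gate is then reported as at or below 2 mm, and state in advance the gate for the remaining patients. Either 2 mm or 3 mm is defensible: 3 mm keeps the protocol's 1 mm buffer, while 2 mm uses the gate just shown to be workable in only five patients. The choice is the sponsor's.

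The cost is wording, with no extra patients or procedures. The study team should confirm that beam-on time can be obtained from existing records, and add it to the recorded items only if it cannot. If attempts are to be reported descriptively, they must be recorded too, since Section 9 does not list them. The downside is that, without the attempts condition, the reduction may stop earlier than under Section 1 and give a wider reported minimum gate.

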13.0 CRITERIA FOR REMOVAL FROM STUDY

1. Found to be ineligible for the protocol as described in the section on Criteria for Patient/Subject Eligibility
2. Patient and/or guardian requests to withdraw from study for any reason
3. Referring physician requests to withdraw from study for any reason, including believing that it would be in the patient's best interest
4. Refusal of patient to continue treatment and/or observations
5. Loss to follow-up
6. Patient death
7. Calypso beacon migration of >5cm from original implantation position may be taken off study if the Calypso signal can no longer be detected
8. Patient unable to adequately perform the breath hold for 3 consecutive treatment days

Acquired data from patients who would be removed from the protocol after a portion of the treatment has been completed can be used for analysis.

14.0 BIOSTATISTICS

The primary objective of this nonrandomized study is to test the feasibility of anchored Calypso transponders to guide and monitor DIBH radiation treatments. Feasibility is defined as patients being able to successfully complete the course of treatment. Patients who cannot have their transponders placed accurately bronchoscopically and for whom Calypso-guided DIBH will not be possible as a consequence of that will be considered a failure. Patients who are removed from the protocol as a result of being unable to perform the breath hold for 3 consecutive treatment days at any point in the treatment course for reasons that are not related to the Calypso transponders, Calypso detection or complications of using the Calypso implantation or system (e.g. disease progression, severe side effects from treatment, e.g. esophagitis, infections, failure to thrive, generalized weakness, low blood counts etc.), will be replaced by new evaluable patients. The patients who are removed will be treated with the free-breathing backup radiation treatment plan. The reason for the patient's inability to hold their breath will be recorded.

For this objective the first and second set of 25 evaluable patients will be stratified and analyzed separately. Some details are provided below.

We will enroll 30 patients upfront and we expect that at least 25 evaluable (DIBH training can be done and Calypso beacons can be implanted without migrating > 5cm) patients can be used in

assessing the feasibility rate. To establish the decision rule we will compute the sample feasibility rate (i.e., the number of patients who could be successfully treated divided by the total number of evaluable patients, which we expect to range from 25 to 30) and form an 80% 2-sided Clopper-Pearson exact confidence interval. If the lower bound of this exact confidence interval is greater than 66% then we will declare this procedure feasible. Namely, we will test the hypotheses $H_0: \theta \leq 0.66$ vs. $H_1: \theta > 0.66$ at $\alpha=0.05$, where θ denotes the feasibility rate. The test statistic will be the lower bound of the 90% 2-sided Clopper-Pearson exact confidence interval for binomial trials. Equivalently, this test statistic can be written as $\text{Beta}(0.05, X, N+1-X)$, i.e., the 5th-percentile of the beta distribution with two parameters X and $N+1-X$, where X and N denote the number of successes and the total sample size (expected to be from 25 to 30), respectively. When the sample size is as small as 25, the power of rejecting the null hypothesis is 61%, 84% and 97% when the true feasibility rate is 0.80, 0.85 and 0.90, respectively. When the sample size is as large as 30, such power becomes 61%, 85% and 97%. Since we expect the feasibility rate to be around 0.85, the sample size is sufficiently large. We expect to finish the recruitment in 4 years.

For protective purposes we will implement a stopping rule to prevent excessive rate of pneumothorax or hospitalization (related to the proposed procedure). If 6 or more events (i.e., procedure-related pneumothorax or hospitalization) among the first 30 patients, or 11 or more events among the total 55 patients we plan to enroll are observed, we will halt the trial to thoroughly investigate such events. This sequential stopping rule has the following probability of halting the trial:

True event probability	0.05	0.08	0.10	0.15	0.20	0.25	0.30
Probability of halting the trial	0.003	0.030	0.081	0.342	0.679	0.900	0.978

In addition, a second stopping rule will be implemented if a maximum of two device migrates to a critical organ, such as the heart or brain, or if one device-related death is observed.

For the 1st secondary objective, we will compare the visual vs no visual biofeedback treatments (for patients who agree to use the digital goggles) by the number of treatment interruptions. We expect that there will be fewer treatment interruptions when using biofeedback. To this end Wilcoxon signed-rank tests will be conducted based on the patients who can successfully be treated.

For the 2nd secondary objective, we will assess differences in the ability of maintaining the DIBH maneuver within the fate with and without visual biofeedback. Such differences will be measured as duty cycle, and will be compared using Wilcoxon signed-rank tests based on the patients who can successfully be treated.

For the 3rd secondary objective, the residual intrafraction tumor motion (surrogated by Calypso) will be measured in all 3 dimensions and the euclidean distance will be calculated, which will then be correlated with the normal tissue dosimetry (see end of Section 12.0). Patients will receive multiple fractions and thus multiple measurements of such distance will be obtained from the same patients.

These repeated measures will be averaged for each patient and the correlation will be examined by simple linear regression. If such continuous data are skewed, we may either use an appropriate monotone transformation, or examine the nonparametric correlation coefficient (such as Spearman rank correlation coefficient) between the tumor motion and the normal tissue dosimetry instead.

For the 4th secondary objective, the potential increase in dose escalation and decrease in margins made possible by Calypso- guided DIBH, as contrasted to those obtained from the 40 CT scan, will be formulated as pair data from each patient and tested by using Wilcoxon signed-rank tests. Dosimetric parameters listed at the end of Section 12.0 will be used again for such analysis.

The 5th secondary objective does not require statistical analysis. See Section 12.0 for details.

For the 6th secondary objective, tumor shrinkage, beacon position and centroid changes in conventionally fractionated patients (totally 10), all measured as continuous variables, will be summarized descriptively.

For the 7th secondary objective, intra- and inter-fraction variation in lung volume preservation of multiple DIBH maneuvers will be recorded within each patient and summarized descriptively.

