9.0 TREATMENT/INTERVENTION PLAN

Using ENB and rEBUS, three Calypso transponders will be bronchoscopically placed within a small bronchial airway according to the Anchored Beacon Transponder Instructions for Use provided by Varian Medical (see section 20.0 Appendices). Two Calypso transponders will be permissible if it is technically not possible to place three transponders, as the tracking system works with a minimum of two transponders. Placement within 2 cm from the pleura should be avoided if possible to minimize the risk of pneumothorax. The position of the anchored transponders will be verified by fluoroscopy at the time of placement.

After a minimum of 3 days, the patient will be brought to the radiation simulation suite and immobilized using a custom-mademold, as per our standard protocol. Immobilization will be in a supine position unless prone treatment is required to meet the distance requirement

between the Calypso beacons and the Calypso detector plate. The patient will be coached through the DIBH maneuver and a breath-hold level that the patient can comfortably and reproducibly achieve using the Calypso system will be determined. A free-breathing (FB) 4D CT scan of the thorax and a CT scan in DIBH mode will be obtained using the RPM system. The patient's position and setup will be documented by tattoos and photographs.

Target volumes and normal structures will be delineated on the FB scan and on the DIBH scan. Target delineations will be performed on the registered 4DCT image set and on the DIBH scan as per current clinical practice. The Calypso beacons will also be delineated on each phase of the 4DCT study and on the DIBH scans.

Analysis of the 4DCT will provide an initial evaluation of the motion concordance between the Calypso beacon and the RPM external marker. Two radiation treatment plans will be developed, one based on the free-breathing scan and one based on the DIBH scan. These will be used for dosimetric comparison of treatment plans between a free-breathing and DIBH treatment. Only the DIBH treatment plan will be used clinically, unless a patient is unable to complete the DIBH maneuvers at the time of treatment. In that case, the plan based on the FB scan will serve as a backup plan. The beacon coordinates for the DIBH scan will be input to the Calypso system.

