12.0 CRITERIA FOR THERAPEUTIC RESPONSE/OUTCOME ASSESSMENT

Primary objectives:

- To evaluate the feasibility of Calypso transponders as an internal tumor surrogate to guide DIBH radiation treatments in real time.
- Feasibility is defined as completion of all treatments using the DIBH treatment plan and Calypso transponders. Patients who cannot have their transponders placed accurately bronchoscopically or for whom Calypso-guided DIBH will not be possible will be considered a failure. Patients who are removed from the protocol as a result of being unable to perform the breath hold for 3 consecutive treatment days at any point in the treatment course for reasons that are not related to the Calypso transponders, Calypso detection or complications of using the Calypso implantation or system (e.g. disease progression, severe side effects from treatment, e.g. esophagitis, infections, failure to thrive, generalized weakness, low blood counts etc.), will be replaced by new evaluable patients. Those patients will be treated with the free-breathing backup radiation treatment plan. The reason for the patient's inability to hold their breath will be recorded.

Secondary objectives:

- To compare the reproducibility with visual versus without visual biofeedback.
- To assess differences in the ability of maintaining the DIBH maneuver within the fate with and without visual biofeedback
- To measure the residual intrafraction tumor motion and associated improvement in normal tissue dosimetry during DIBH based on the Calypso lung transponder signal as a surrogate

- To measure the increase in dose escalation and the potential for decreasing margins made possible by Calypso-guided DIBH
- To determine the minimum clinically feasible gate margin for radiation
- To assess tumor shrinkage, beacon position and centroid changes in conventionally fractionated patients
- To assess intra- and inter-fraction variation in lung volume preservation of multiple DIBH maneuvers

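### Sections 12 and 14 define the primary feasibility endpoint differently, and Section 14 leaves unclassified an evaluable patient with well-placed beacons whose Calypso-guided DIBH fails for a Calypso-related reason

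*Combined protocol and SAP*

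**What the plan says.** Two current sections of the combined protocol and SAP define the primary endpoint.

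- **Section 12.0 (outcome assessment), success:** "Feasibility is defined as completion of all treatments using the DIBH treatment plan and Calypso transponders".
- **Section 12.0, failure:** "Patients who cannot have their transponders placed accurately bronchoscopically or for whom Calypso-guided DIBH will not be possible will be considered a failure".
- **Section 14.0 (biostatistics), success:** "Feasibility is defined as patients being able to successfully complete the course of treatment".
- **Section 14.0, failure:** patients whose transponders cannot be placed accurately by bronchoscopy "and for whom Calypso-guided DIBH will not be possible as a consequence of that will be considered a failure".

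Both sections replace patients who are removed after three consecutive days without an adequate breath hold, provided the removal was "for reasons that are not related to the Calypso transponders, Calypso detection or complications of using the Calypso implantation or system".

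Section 14.0 gives the primary statistic as "the number of patients who could be successfully treated divided by the total number of evaluable patients". It describes evaluable patients as "evaluable (DIBH training can be done and Calypso beacons can be implanted without migrating > 5cm". Feasibility is declared if the exact lower confidence bound exceeds 66%.

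Section 9.0 provides a route to finishing radiotherapy without DIBH. If a patient cannot complete the DIBH maneuvers at treatment, "In that case, the plan based on the FB scan will serve as a backup plan".

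**The concern.** The two failure rules differ in logic. Under Section 12 either event is enough. Under Section 14 both must occur, and the first must cause the second. The success definitions differ as well: Section 12 names the DIBH plan and Calypso, while Section 14 names neither in its definition.

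The two sections therefore part over a patient in whom placement went well but Calypso-guided treatment then failed, for example because the signal could no longer be used. The primary objective is meant to detect this event. If the analysis follows Section 14, someone has to decide how to count such a patient after the outcome is known, in a single-group study whose result turns on a handful of patients.

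**Working it through.** **Step 1. Classify each kind of patient under both sections.**

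| Patient | Section 12.0 | Section 14.0 |
|---|---|---|
| All treatments completed with the DIBH plan and Calypso | Success | Success |
| Placement inaccurate, so guided DIBH impossible | Failure | Failure |
| Breath-hold removal (3 consecutive days), not related to Calypso | Replaced | Replaced |
| Beacon migration > 5 cm | Outside the rate (not evaluable, Section 14.0) | Outside the rate |
| Placement accurate, no migration > 5 cm, guided DIBH fails for a Calypso-related reason, finishes on the free-breathing plan | Failure | No rule applies |

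Only the last row differs. Section 14's failure rule does not reach this patient because placement was accurate, and replacement does not apply because the cause is Calypso-related. The numerator wording (could be successfully treated) does not say on which plan.

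Section 14's denominator adds to the gap. Evaluable patients already have beacons implanted, so the one failure category that Section 14 lists falls largely outside the rate.

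**Step 2. Reproduce the plan's own figures.** The lower bound is Beta(a, X, N+1−X), with a = 0.10 for the 80% interval and a = 0.05 for the 90% interval. The cut-off is the smallest X with a bound above 0.66. Power is P(Bin(N, p) ≥ cut-off).

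| Interval | N | Cut-off | Power at 0.80 / 0.85 / 0.90 | Plan states |
|---|---|---|---|---|
| 80% | 25 | 20 | 61.7% / 83.8% / 96.7% | 61 / 84 / 97 |
| 80% | 30 | 24 | 60.7% / 84.7% / 97.4% | 61 / 85 / 97 |
| 90% | 25 | 21 | 42.1% / 68.2% / 90.2% | – |
| 90% | 30 | 25 | 42.8% / 71.1% / 92.7% | – |

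The stated power matches the 80% interval to within a percentage point and does not match the 90% interval. Section 14 names both intervals. That is a separate inconsistency, so both cut-offs are carried here.

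**Step 3. Effect of one reclassified patient at the cut-off.**

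- N = 25, 80% interval: 19 successes give 0.617 (not feasible); 20 give 0.660 (0.6603 unrounded, feasible).
- N = 25, 90% interval: 20 give 0.625 (not feasible); 21 give 0.670 (feasible).
- N = 30, 80% interval: 23 give 0.639; 24 give 0.675.
- N = 30, 90% interval: 24 give 0.643; 25 give 0.681.

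**Step 4. Sensitivity, resting on an assumption.** Let f be the share of Section 12 failures that fall in the last row of the Step 1 table and are counted as successes. The documents give no value for f. The apparent rate is θ + f(1 − θ). Take θ = 0.66, the null value, and N = 25:

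| f (assumed) | Apparent rate | P(declare feasible), ≥ 20 of 25 | P(declare feasible), ≥ 21 of 25 |
|---|---|---|---|
| 0 | 0.660 | 9.9% | 4.0% |
| 0.10 | 0.694 | 17.6% | 8.1% |
| 0.25 | 0.745 | 35.7% | 19.8% |
| 0.50 | 0.830 | 75.8% | 57.6% |
| 0.75 | 0.915 | 98.4% | 94.4% |

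This shows how the error rate would respond if such patients were counted as successes. It does not forecast how many there will be.

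**The case against.** A reader might infer that Section 14 makes free-breathing completion a success. The documents do not support that. Section 14 opens by stating the objective as feasibility of Calypso transponders for guiding and monitoring DIBH treatment, so the course of treatment can fairly be read as the Calypso-guided DIBH course. No sentence credits completion on the backup plan. Section 9.0 describes patients taken off protocol before completion as receiving the free-breathing plan for the remainder, which points away from success. Limiting replacement to causes unrelated to Calypso also suggests that Calypso-related removals stay in the rate as failures. This stands as inference only: Section 14 never says it, and falling outside a failure rule does not make a patient a success either. The accurate description is unclassified, or open to being counted as a success.

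A reader might also apply the conflict to every patient who cannot manage guided DIBH. That goes too far. Breath-hold removals unrelated to Calypso are replaced under both sections, and migration beyond 5 cm makes a patient non-evaluable.

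Finally, one patient at the cut-off changes the result of any binomial rule, so Step 3 says nothing about frequency. In the related trial cited in Section 3.1.1, two of 48 evaluable patients had one migrated marker each, without effect on tracking. The event may be uncommon. That limits the likely size of the effect but does not remove the conflict.

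**Conclusion.** The inconsistency is real and unreconciled. Both texts are current, both concern the primary endpoint, and the looser one sits in the section that governs the calculation. It affects a narrow group: evaluable patients with accurate placement, no migration beyond 5 cm, and a Calypso-related failure of guided DIBH. For them Section 12 gives a definite answer and Section 14 gives none.

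One such patient is enough to change the conclusion when the count is at the cut-off, under either interval. Any larger effect depends on an assumed share that the documents do not supply. The wording conflict itself is certain. That free-breathing completions would in fact be counted as successes is possible under Section 14's text but not established by it. Because the conflict bears directly on the primary conclusion and is cheap to remove, it should be settled before the analysis.

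**What to change.** Use one definition in both sections, taken from Section 12:

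1. In Section 14, define success as all treatments completed using the DIBH plan and Calypso.
2. In Section 14's failure sentence, replace *and* with *or* and delete the clause that makes the second event a consequence of the first.
3. Add that an evaluable patient who does not complete the course with Calypso-guided DIBH counts as a failure, unless the existing replacement rule for breath-hold removal unrelated to Calypso applies. The exception is needed: a sentence failing every patient who moves to the backup plan would contradict a rule on which both sections agree.

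Every evaluable patient is then a success, a failure or replaced. The change affects analysis wording only and leaves treatment as it is. It costs a few sentences in Section 14, and the downside is a possibly less favourable feasibility rate.
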